5.2 Secondary Endpoints

Table 2 displays the visit windows for evaluation time points that would be used for summarizing the KSS and the VR-12 endpoints. Based on this, for situations in which two or more KSS or VR-12 observations present at a given visit, the observation closest to the upper range of the window would be selected for summary purposes for the visit.

Table 2. Summary of visit windows used for summarizing KSS and VR-12 endpoints

Month	Range of Days (windows) for Month Membership for follow-up post-surgical implantation
6 Months	≤ 182 days
12 Months	>182 to ≤ 365 days
18 Months	>365 to ≤ 548 days
24 Months	>548 to ≤ 730 days
30 Months	>730 to ≤ 913 days
36 Months	>913 to ≤ 1095 days

The secondary endpoints are as follows:

- Two-year (24 months) postoperative visit Knee Society Score (KSS).

CONFIDENTIAL AND PROPRIETARY

[figure not shown]
This document contains information that is confidential and proprietary to Smith & Nephew PLC and Smith & Nephew, Inc. and is intended for use only by Smith & Nephew and its manufacturer. It shall not be reproduced or copied in whole or in part, nor shall the contents be disclosed by any means without prior written permission from Smith & Nephew, nor shall anyone make any use of it that is contrary to the expressed or implied wishes of Smith & Nephew.

Statistical Analysis Plan	 Number: 16-NPFS-11 Version: Final 1.0, Jan 29, 2018 Page: 10 of 25
A Retrospective Study of the NAVIO Robotic-assisted Surgical System	

- Two year (24 months) post-operative visit VR-12 domain and sub-domain scores. These scores would encompass the individual domains of physical component score (PCS), mental component score (MCS) as well as the sub-domain scores within the PCS (physical functioning, role physical, bodily pain, and general health) and those within the MCS (vitality, social functioning, role emotional, and mental health).
- Anterior/Posterior and lateral radiographic assessments which include but not only restricted to the following:
 - Radiographic findings
 - Component orientation
 - Radiolucencies
 - Migration
 - Osteolysis
 - Stress shielding
 - Subsidence

CONFIDENTIAL AND PROPRIETARY

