7.14 Other Data Summaries

- The type of analysis carried out on the primary endpoint, the Kaplan-Meier estimates would be summarized non-inferentially for the following subgroups using the safety population:
 - Age (< 60 years versus \geq 60 years),
 - BMI (< 30 kg/m² versus \geq 30 kg/m²)

CONFIDENTIAL AND PROPRIETARY

This document contains information that is confidential and proprietary to Smith & Nephew PLC and Smith & Nephew, Inc. and is intended for use only by Smith & Nephew and its manufacturer. It shall not be reproduced or copied in whole or in part, nor shall the contents be disclosed by any means without prior written permission from Smith & Nephew, nor shall anyone make any use of it that is contrary to the expressed or implied wishes of Smith & Nephew.

Statistical Analysis Plan	 smith&nephew
A Retrospective Study of the NAVIO Robotic-assisted Surgical System	Number: 16-NPFS-11
	Version: Final 1.0, Jan 29, 2018
	Page: 24 of 25

- Sex (males versus females), and
- Region (Europe versus USA).

For the subgroup analysis by region, investigational sites within Europe would be pooled into one virtual site and all investigational sites within the USA would be pooled into another virtual site.

- Other data summaries that would be performed using the safety population, are as follows:
 - Shift from baseline to 2 years (24 months) in overall physical health,
 - Shift from baseline to 2 years (24 months) in overall emotional problems.
- Subject discharge data would be summarized descriptively using the safety population for length of hospital stay prior to discharge (days) as a continuous variable and using categorical summary statistics (n and %) for place discharged to and primary ambulatory support prior to discharge.
- Listing of medical history.
- Summary of KSS and VR-12 derived endpoints at 6 months, 12 months, 18 months, 30 months and 36 months.

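### SAP Table 2 windows for KSS and VR-12 look back only, so a late 6-, 12- or 18-month visit takes the next label and a lone early score is reported as 6 Months

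*SAP*

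**What the plan says.** SAP 5.2, Table 2, defines six consecutive postoperative windows for summarising KSS and VR-12. The first is "6 Months ≤ 182 days", which has no lower limit. Each of the other five opens where its predecessor closes; the second, for instance, is ">182 to ≤ 365 days". The remaining four close on days 548, 730, 913 and 1095, and nothing is defined beyond the last of these.

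Where two or more scores fall in one window, "the observation closest to the upper range of the window would be selected for summary purposes for the visit".

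The rows other than 24 Months are used in SAP 7.14, which lists "Summary of KSS and VR-12 derived endpoints at 6 months, 12 months, 18 months, 30 months and 36 months". SAP 7.11 analyses secondary endpoints as observed cases without imputation. Protocol 3 and 6.2 take interim scores from whatever postoperative follow-up the records hold; no interim visit days are fixed.

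**The concern.** A visit window normally has room on both sides of its target day. Here each window runs from the previous nominal day up to its own, so a visit even one day late belongs to the next time point. The first window runs from surgery to day 182, so a score from the first weeks of recovery can stand under a 6-month label.

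Protocol 2 includes change in clinical, functional and quality-of-life outcomes over time among what the study is to show. SAP 7.15 drops change from baseline for KSS and VR-12 because baseline was missing in all 27 subjects analysed at that point. The by-visit summaries are therefore much of what is left to describe those scores over time, and readers will take the row labels at face value.

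**Working it through.** **1. Windows against nominal days.** Inputs are the Table 2 limits. Nominal day = months × 365/12.

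| Row | Days covered | Nominal day | Upper limit minus nominal |
|---|---|---|---|
| 6 Months | up to 182 | 182.5 | −0.5 |
| 12 Months | 183–365 | 365 | 0 |
| 18 Months | 366–548 | 547.5 | +0.5 |
| 24 Months | 549–730 | 730 | 0 |
| 30 Months | 731–913 | 912.5 | +0.5 |
| 36 Months | 914–1095 | 1095 | 0 |

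Each window has about 182 days before its nominal day and, to within a day, none after it. With 365.25/12 the differences are still under one day.

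**2. Literal assignment.**
- Day 182 goes to 6 Months, and day 183 to 12 Months.
- Day 365 goes to 12 Months, and day 366 to 18 Months.
- Day 548 goes to 18 Months, and day 549 to 24 Months.
- Days 14, 42 and 90 all go to 6 Months.
- Day 1096 goes to no row.

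**3. The tie-break.** Take scores on days 42, 190 and 360. Day 42 is alone in the first window and becomes the 6 Months value. Days 190 and 360 share the second window; day 360 is closer to 365 and is chosen. The 6-month score of day 190 then appears in no row. Without the day-360 score, day 190 would be the 12 Months value.

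**4. How many visits could be affected.** The documents give no interim visit days, so this needs assumptions.

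(a) Visits spread evenly within ±k days of the upper limit. The share after the limit is k/(2k+1): 14/29 = 48%, 30/61 = 49%, 45/91 = 49%.

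(b) Visits normally distributed around the week-based points in SAP 7.10 (24, 48 and 72 weeks, that is days 168, 336 and 504). The share after the limit is 1 − Φ((limit − centre)/SD).

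| Visit | Limit − centre | SD 14 days | SD 30 days |
|---|---|---|---|
| 6 months | 182 − 168 = 14 | 16% | 32% |
| 12 months | 365 − 336 = 29 | 2% | 17% |
| 18 months | 548 − 504 = 44 | about 0% | 7% |

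(c) Visits averaging 14 days after the limit. The share is Φ(14/SD): 84% with SD 14 and 68% with SD 30.

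The assignments in steps 2 and 3 need no assumption. Only the shares in step 4 do.

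**The case against.** The strongest reply is about weight. The interim rows appear in one item under other data summaries, are descriptive, and feed no hypothesis or success rule. That stands, and it keeps the point modest.

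The SAP's own week-based time points lie 14, 29 and 44 days inside the first three windows, so most visits centred there would keep their label. SAP 7.10 applies those points to the Kaplan-Meier estimates, not to KSS or VR-12, so they do not repair Table 2. They do show that the share mislabelled depends on where visits centre.

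The tie-break also gives some protection: an early score fills the 6 Months row only when no later score exists by day 182.

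A reader might go further and infer that about half of the 6 Months row would be 6-week scores, or that the 18 Months row would consist of late 12-month visits. Simulation gives such results (about 49% for the first) if every subject is scored at 6 weeks and at 6, 12 and 24 months, with visits centred on the nominal day. The documents give no such schedule, and the absence of an 18-month visit from it produces the second result by construction. Nor do they support a claim that function would be understated by a known amount, which needs an assumed recovery curve.

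**Conclusion.** The rule as written mislabels scores: a 6-, 12- or 18-month visit one day past the window limit takes the next label or drops out, and a lone early score is reported as 6 Months. No other rule in either document corrects this.

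The effect on the interim time points is confined to the descriptive summaries in SAP 7.14. The primary endpoint and its test are unaffected. The 24-month row has the same shape: a lone day-549 score enters it and a day-731 score leaves it. It therefore cannot be left out of the repair.

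The share mislabelled is unknown. About half is the figure if visits centre on the nominal day, and 16-32% at 6 months and 2-17% at 12 months if they centre on 24 and 48 weeks with SD 14-30 days. It would be higher if visits tend to run late.

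**What to change.** Before database lock, replace all rows of Table 2 together with contiguous windows split at the midpoints between nominal days, (months ± 3) × 365/12:

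| Row | Days |
|---|---|
| Early postoperative | before 92 |
| 6 Months | 92–273 |
| 12 Months | 274–456 |
| 18 Months | 457–638 |
| 24 Months | 639–821 |
| 30 Months | 822–1004 |
| 36 Months | 1005–1186 |

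Day 1004 is equidistant from days 913 and 1095 and is placed in 30 Months by convention. When several scores fall in one window, select the one closest to the nominal day. A visit 14 days late (days 196, 379, 562, 744 or 927) then keeps its own label, and day 42 leaves the 6 Months row.

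The 24-month row has to move with the rest. If it stayed at days 549–730, the 18-month window would still stop on its nominal day, and a 30-month row starting at day 822 would leave days 731–821 in no row. Its new start, day 639, is 730 − 91, which matches the protocol's allowance of three months before two years. The protocol sets no upper limit on the 2-year score, and that should be kept for the 2-year endpoint, so that a visit after day 821 still counts there whatever its by-visit row.

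The cost is a few lines of SAP text and the visit-mapping code, with no new data. The downside is one extra row, and fewer observations under 6 Months where only early scores exist.

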**Protocol Synopsis:**

Title of Study:	A Retrospective Study of the Navio ◊ Robotic-assisted Surgical System
Study Type:	Post-market
Study Device:	Navio ◊ Robotic-assisted Surgical System
Indications	Navio System-assisted Unicondylar Knee Replacements (UKR) are indicated for restoring either compartment of a knee that has been affected by: 
 
• Non-inflammatory degenerative joint disease including osteoarthritis, traumatic arthritis, or avascular necrosis
 
• Correction of functional deformity
 
• Treatment of fractures that are unmanageable using other techniques
 

Study design:	A retrospective, multi-center, cohort study with prospective follow-up and comparison to historical control
Primary Endpoint:	Navio System assisted Unicondylar Knee Replacement (UKR) revision rate 2 years postoperative
Secondary Endpoints:	Given the retrospective-prospective study design, secondary endpoint data will be collected to the extent that it is available and will include: 
 
• Change in Knee Society Score (KSS) from baseline to 2 years (-3months) or greater postoperative
 
• Change in VR12 from baseline to 2 years (-3months) or greater postoperative
 
• Anterior/Posterior and lateral radiographic assessments
 

Safety Assessment:	Study device and procedure-related adverse events (AE) incidence and frequency
Length of Study:	Up to 1 year: includes enrollment phase and collection of a minimum of 2-year postoperative follow-up data
Study Visits:	Retrospective pre-operative, operative and any available postoperative follow-up; Prospective 2-year or greater postoperative follow-up
Number of Sites:	Up to 10 sites in the United States and Europe
Sample Size:	One hundred twenty-eight (128) subjects, including 10% inflation to allow for attrition
Inclusion Criteria:	
 
1. Male or female subjects ≥18 years old (at the time of surgery) who have undergone Navio System-assisted UKR prior to IRB/EC site approval. This includes UKR procedures with all Unicondylar Knee cemented implant designs.
 
2. Subject had a primary diagnosis of unicompartmental, non-inflammatory degenerative joint disease including osteoarthritis, traumatic arthritis, or avascular necrosis, required correction of functional deformity, or required treatment of fractures that were unmanageable using other techniques.
 

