## 2.2. Secondary Endpoints

Given the retrospective-prospective study design, secondary endpoint data will be collected to the extent that it is available and will include:

- Change in Knee Society Score (KSS) from baseline to 2 years (-3months) or greater postoperative
- Change in VR12 from baseline to 2 years (-3months) or greater postoperative
- Anterior/Posterior and lateral radiographic assessments:
  - Radiographic findings
  - Component orientation
  - Radiolucencies
  - Migration
  - Osteolysis
  - Stress shielding
  - Subsidence

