## 3. STUDY DESIGN

This is a retrospective, multi-center, cohort study with prospective follow-up and comparison to historical control to collect 2-year safety and effectiveness data on 128 subjects, at up to 10 sites in the United States and Europe, who have undergone Navio System-assisted UKR.

Subject data will be retrospectively evaluated at the pre-operative, operative, and any available postoperative follow-up visits as well as prospectively evaluated at the 2-year (-3months) or greater postoperative follow-up visit.

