#### **5. STUDY POPULATION**

##### **5.1. Subject Screening and Enrollment**

To eliminate the potential for selection bias, Investigators will consecutively screen subjects by date of surgery, starting with their first Navio-assisted UKR subject. For screening, only information in the medical records will be reviewed. Subjects meeting all eligibility criteria will be listed on a Screening and Enrollment log.

Once a subject has completed the informed consent process, if required by the IRB/EC, the subject will be considered enrolled and assigned a consecutive Subject Identification (ID) number that identifies a single study knee. The subject ID number will be listed on the Screening and Enrollment Log. In the event that a subject has bilateral Navio assisted UKR, only the first treated knee will be enrolled and assigned a Subject ID. The Screening and Enrollment Log is the source in which records all screening and enrollment details are recorded.

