### **6.3. Prospective Data Collection: 2-Year (-3 months) or Greater Postoperative Follow-up**

Collect the following prospective data for subjects who have not retrospectively completed a 2-year (-3months) or greater postoperative visit and consent to participate in the prospective phase of the study:

- Implant Status
- KSS
- VR-12
- Anterior/Posterior and lateral radiographs and assessments:
  - Radiographic findings
  - Component orientation
  - Radiolucencies
  - Migration
  - Osteolysis
  - Stress shielding
  - Subsidence
- Revision CRF, if applicable
- End of Study CRF
- Study Device and Procedure-Related Adverse Events

The prospective follow-up visit may occur in an office or remotely. If completed remotely (e.g. telephone call, mailing of subject questionnaires and/or any other means), secondary endpoint data will be collected to the extent possible.

If the subject already completed the 2-year visit at the time of enrollment, 2-year visit data will be collected retrospectively as defined in section 6.2.

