SAP	Statistical Analysis Plan
SF-12	Short Form 12 Health Survey Standard
TFL	Tables, Figures, and Listings
UADE	Unanticipated Adverse Device Effect(s)
UKR	Unicompartmental Knee Replacement
VR-12	Veterans RAND 12 Item

CONFIDENTIAL AND PROPRIETARY

This document contains information that is confidential and proprietary to Smith & Nephew PLC and Smith & Nephew, Inc. and is intended for use only by Smith & Nephew and its manufacturer. It shall not be reproduced or copied in whole or in part, nor shall the contents be disclosed by any means without prior written permission from Smith & Nephew, nor shall anyone make any use of it that is contrary to the expressed or implied wishes of Smith & Nephew.

Statistical Analysis Plan	 smith&nephew
A Retrospective Study of the NAVIO Robotic-assisted Surgical System	Number: 16-NPFS-11
	Version: Final 1.0, Jan 29, 2018
	Page: 6 of 25

2. Introduction

This statistical analysis plan (SAP) is written to specify the statistical analyses that would be carried out for study protocol 16-NPFS-11 in greater detail than the protocol. The statistical details provided herein would serve as guideline for the programming that would generate this study's tables, figures, and listings (TFLs).

The SAP is based on version 2.0 of the protocol dated 05 June 2017 and version 3.0 of the study's accompanying case report forms (CRFs).

3. Study Design

The NAVIO system is designed to assist surgeons in providing software-defined spatial boundaries for orientation and reference information to anatomical structures during orthopedic surgical procedures.

This study is a retrospective, multi-center, cohort study to be carried out on approximately 128 subjects enrolled at up to 10 investigational sites. These subjects would have previously undergone the NAVIO System-assisted Unicondylar Knee Replacement (UKR) for restoring either compartment of the knee that has been affected by any of the following conditions: (a) Non-inflammatory degenerative joint disease including osteoarthritis, traumatic arthritis, or avascular necrosis (b) Correction of functional deformity and (c) Treatment of fractures that are unmanageable using other techniques.

CONFIDENTIAL AND PROPRIETARY

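### The SAP's 24-month window for KSS and VR-12 (days 549–730) differs from the protocol's window of two years less three months with no upper limit, and SAP 7.15 does not declare the change

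*SAP*

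**What the plan says.** Protocol 2.2 defines the KSS endpoint as "Change in Knee Society Score (KSS) from baseline to 2 years (-3months) or greater postoperative" and uses the same timing for VR-12. Section 3 says subjects are "prospectively evaluated at the 2-year (-3months) or greater postoperative follow-up visit". Section 6.3 reserves that visit for "subjects who have not retrospectively completed a 2-year (-3months) or greater postoperative visit". The synopsis also leaves the visit open-ended: "Prospective 2-year or greater postoperative follow-up".

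SAP 5.2 makes the 24-month visit the secondary endpoint for KSS and VR-12. Table 2 sets that visit at ">548 to ≤ 730 days", followed by a 30-month band to day 913 and a 36-month band to day 1095, with no band after that. When a subject has several observations in a band, "the observation closest to the upper range of the window would be selected for summary purposes for the visit".

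SAP 7.11 describes the KSS visit as two-plus years but gives no rule that admits visits after day 730. SAP 7.14 places the 30- and 36-month summaries among other data summaries. SAP 7.15 declares two changes from the protocol: the full analysis set is no longer referred to, and 24-month values replace change from baseline.

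**The concern.** Table 2 decides which observation counts as the two-year value. Its 24-month band opens about three months earlier than the protocol allows and closes where the protocol has no limit. Because the secondary endpoints are analysed as observed cases without imputation, the band alone determines who is in the two-year KSS and VR-12 summary and at what follow-up time.

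The study design makes late visits plausible. Protocol 5.1 has sites screen consecutively, "starting with their first Navio-assisted UKR subject", so early cases may be well past two years at enrolment. A subject already past day 730 with no qualifying visit on record can be seen prospectively only after day 730. The visit the protocol arranges to obtain the two-year value then cannot enter the 24-month row. For that subject the row is either empty or holds an observation from days 549–638 that the protocol treats as too early.

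**Working it through.** **1. The SAP's cut-points.** Converting months to days as months × 365/12 gives 18 → 547.5, 24 → 730, 30 → 912.5 and 36 → 1095. Table 2 has 548, 730, 913 and 1095, so its bounds are reproduced to within half a day. Each band covers the six months before its label and ends at the label.

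**2. The protocol's lower limit.** 24 − 3 = 21 months.
- 21 × 30.4375 = 639.2 days
- 730 − 91 = 639 days
- Counting calendar months from every surgery date between 1 January 2012 and 5 June 2017 (an assumed range): 638 to 642 days

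Day 639 is used below. The protocol gives no upper limit.

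**3. Overlap, in whole days.**
- SAP 24-month band: 730 − 549 + 1 = 182 days
- Too early under the protocol: 638 − 549 + 1 = 90 days; 90/182 = 49% (89 to 93 days, or 49–51%, over the calendar range)
- Shared: 730 − 639 + 1 = 92 days (89 to 93)

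These are shares of calendar days, not of subjects.

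**4. How a visit is classified.**

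| Visit day | Protocol two-year visit? | SAP Table 2 row |
|---|---|---|
| 549–638 | No, too early | 24 Months, used if there is no later visit by day 730 |
| 639–730 | Yes | 24 Months |
| 731–913 | Yes | 30 Months (7.14 only) |
| 914–1095 | Yes | 36 Months (7.14 only) |
| After 1095 | Yes | None |

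The selection rule limits the first row, since a later observation in the band is preferred. It does nothing for the last three rows.

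**5. The second anniversary.** The SAP does not say whether surgery is day 0 or day 1. If it is day 0, the anniversary is day 730, or day 731 when 29 February 2016 falls in between, which is the case for surgeries from 1 March 2014 to 28 February 2016. The band therefore allows no days after the anniversary, and for those surgery dates a visit exactly at two years is filed under 30 Months.

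**6. Illustration with assumed visit dates.** The documents give no visit dates. Two document dates serve as stand-ins: the SAP is based on "version 2.0 of the protocol dated 05 June 2017" and is itself dated 29 January 2018. Day 731 is the first day outside the 24-month band, and day 1096 the first with no row.

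| Assumed visit | Past day 730 if operated on or before | No row if operated on or before |
|---|---|---|
| 5 June 2017 | 5 June 2015 (−731 days) | 5 June 2014 (−1096 days) |
| 29 January 2018 | 29 January 2016 (−731 days) | 29 January 2015 (−1096 days) |

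**7. Declaration.** Neither change listed in SAP 7.15 mentions the timing of the visit. Replacing change scores by 24-month values is a different matter from redefining which visits are 24-month visits.

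**The case against.** The strongest reply is that nothing inferential depends on Table 2. KSS and VR-12 are summarised descriptively, no test, margin or sample size uses the bands, and the Kaplan-Meier primary analysis does not refer to them. Observations from days 731–1095 are still reported, so only those after day 1095 have no row. Contiguous, non-overlapping bands keep time points distinct, which is a defensible choice. Protocol 9.4 leaves the detail of the summaries to the SAP, Table 2 states its bounds openly, and 7.15 does say that the endpoints are now 24-month values. The two-plus-year wording in 7.11 may mean that later visits were intended to count.

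Much of this stands, and it limits the seriousness. The calendar cut-offs are illustrations and do not show that any subject is affected. The anniversary point moves a visit by one day and depends on an assumed day-0 convention.

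The objection does not remove the mismatch. A value shown at 30 months is still outside the secondary endpoint, and one from days 549–638 is still inside it against the protocol's definition. If later visits were meant to count, Table 2 and 7.11 conflict, and a programmer could produce different tables from each. A closed band can be defended, but that defence would not cover this lower limit, and the SAP offers none for the upper one.

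**Conclusion.** The concern holds. Followed as written, SAP Table 2 summarises a different set of visits from the one the protocol defines: it admits about 90 days that are too early, excludes everything after day 730, and has no row after day 1095. SAP 7.15 does not declare this.

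It should be fixed, but its reach is limited to descriptive secondary summaries; the primary analysis is untouched. The number of subjects affected is unknown. The textual mismatch rests on no assumption beyond converting 21 months to about day 639 (638 to 642). The anniversary result assumes surgery is day 0, and the calendar cut-offs also assume the visit dates.

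**What to change.** **Preferred.** For the KSS and VR-12 secondary endpoints, and for the 24-month shift summaries in SAP 7.14 if they use Table 2:
- Take one observation per subject on or after day 639: the one closest to day 730, and the later one in a tie. The protocol has no rule for choosing among several visits, so the SAP must state one.
- Do not count days 549–638 as 24 months; put them in an earlier or unscheduled row.
- State whether surgery is day 0 or day 1.
- Report the median and range of visit time beside the two-year summary.
- Keep the 30- and 36-month rows as supplementary, with a note that an observation there may also be the subject's two-year value.

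**Alternative.** If the sponsor prefers a closed window, raise its lower limit to about day 639, declare and justify the upper limit in 7.15, and align the two-plus-year wording in 7.11.

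**Cost.** Text changes to SAP 5.2, 7.11 and 7.15 (and 7.14 if applicable) and to the matching table programs; no new data. SAP 7.15 refers to 27 subjects already analysed at an interim, so the amendment should say that the window was revised after that look. The open-ended rule lets a subject's only visit at three or more years enter the two-year summary, as the protocol does, and some observations will appear in two rows. The closed window avoids both but leaves out late visits that the protocol accepts, which is why it must be declared.
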